#### **3.2 Aims of the study**

- To determine if wearing the MS lenses slows the progression of myopia and axial elongation in myopic schoolchildren over 2 years.
- To compare the changes in refractive error (Rx) and axial length (AL) in children wearing MS lens with those children wearing single vision (SV) spectacle lens (control).

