#### 4.11 Statistical analysis

Data of two groups will be presented as the mean  $\pm$  SD. Only data of the right eyes will be used for data analysis if there are high correlation of data between two eyes. Baseline data between two groups between males and female will be analyzed by unpaired t-tests. Welch correction is applied if the difference of SD between the groups is statistically significant.

Primary outcomes

- Changes in auto-refraction (SER in diopters) with cycloplegia

Secondary outcomes

- Changes in axial length (mm) with cycloplegia

1. Repeated measures ANOVAs were used to compare the changes from the baseline visit in SER, and AL over time and between the two study groups in study. Interactions between time and groups were also assessed. If repeated measures ANOVA showed significant results between groups and significant interaction between time and groups, unpaired *t* tests were used to test for differences in SER, AL, between the two groups after the 24-month follow up period, and plots of the change will be plotted for showing trends. Bonferroni corrections were used to take account of *post-hoc* comparisons. The efficacy of myopic control will be determined by dividing the difference in mean SER changes of two groups with the mean SER change in the SV group times 100%.
2. The correlations between changes in Rx, biometric parameters and related factors (e.g. lens wear time, time spent on outdoor activities) are analyzed using Pearson correlations. Multivariate analyses of variance are used to examine the effect on treatment outcomes of various factors, including age, gender, initial refraction, etc.
3. To examine the choroidal response to MD in MS lens, changes in choroidal thickness over time and between two groups will be compared by the same statistically methods used for SER and AL mentioned above (*point 1*). Besides, the correlation between changes in choroidal thickness and axial length will be calculated using Pearson's correlation coefficient. Correlation between the pupil sizes, peripheral refraction and the effect in myopic control in terms of axial length elongation will be calculated using Pearson's correlation coefficient.

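### Correlating pupil size and peripheral refraction with axial elongation cannot show for whom the MS lens works better; that needs a lens-by-factor interaction (cheap improvement)

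*Combined protocol and SAP*

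**What the plan says.** All of this is in section 4.11 of the combined protocol and SAP, except the aims (section 3.2).

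- **Point 3** covers pupil size and peripheral refraction. The quantity to be computed is "Correlation between the pupil sizes, peripheral refraction and the effect in myopic control in terms of axial length elongation", and the stated method is Pearson's. It does not say whether the correlation is pooled, run within MS wearers or run in each arm. Nor does it say which visit's factor value is used or whether the arms are compared.
- **Point 1** defines efficacy between groups, by "dividing the difference in mean SER changes of two groups with the mean SER change in the SV group times 100" percent. The only interaction the plan names is here: "Interactions between time and groups were also assessed".
- **Point 2** covers other factors. "Multivariate analyses of variance are used to examine the effect on treatment outcomes of various factors, including age, gender, initial refraction, etc". No model terms are listed. Wear time and outdoor time are handled by Pearson correlation with the changes in refraction and biometry.
- **Section 3.2** lists no aim about who benefits most. The between-group aim is "To compare the changes in refractive error (Rx) and axial length (AL) in children wearing MS lens with those children wearing single vision" lenses.

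**The concern.** Point 3 asks about the lens's effect, but the variable it correlates is elongation. By the plan's own definition in point 1, efficacy is a contrast between two groups, and a single child has no such value. A factor that predicts natural growth equally under both lenses will correlate with elongation even if the lens helps every child by the same amount. Conversely, a factor that truly changes the lens effect can show no correlation in the set of children examined.

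At stake is a secondary statement, for example that the lens works better in children with larger pupils or a certain peripheral refraction. The planned analysis could produce such a statement from prognosis alone, or fail to find a real one.

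**Working it through.** **Inputs from section 4.3.** Difference 0.50 D, SD 0.6 D, two-sided alpha 0.01, power 90%, 43 completers per group, dropout about 40%, 90 recruited per group.

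**The plan's own figure.** n = 2 × [0.6 × (2.576 + 1.282) / 0.50]² = 42.85, rounded up to 43. Dividing by 0.6 gives 72. A t-based calculation needs 45, and 45 / 0.6 = 75. The stated 43 and 72–75 are reproduced. No sample-size figure is given for the factor analyses.

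**Inputs to the check.** Completers: 90 × 0.6 = 54 per arm. Lens effect: 0.50 / 0.6 = 0.83 SD. This is the SER figure, used because the documents give no effect or SD for axial length. Test level: two-sided 5%, an assumption, since section 4.11 states none for these correlations. The strength of the factor is also an assumption, because the documents give none.

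**A. Factor is prognostic only (same slope in both arms, no effect modification).** By Fisher's z, the rejection rate is about Φ(atanh(r) × √(N − 3) − 1.96), plus a small opposite tail.

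- Within MS wearers, r = 0.3, N = 54: 0.3095 × √51 = 2.210; Φ(0.250) = 60%.
- Pooled, N = 108: the lens difference adds 0.83² / 4 to the variance, so the SD grows by √1.1736 = 1.083 and r falls to 0.3 / 1.083 = 0.277. Then 0.2843 × √105 = 2.914; Φ(0.954) = 83%.

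| Assumed within-arm r | Pooled | MS only | Interaction test (simulated) |
|---|---|---|---|
| 0 | 5% | 5% | 5% |
| 0.1 | 16% | 11% | 5% |
| 0.2 | 48% | 30% | 5% |
| 0.3 | 83% | 60% | 5% |

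Simulation of 20,000 trials per row agrees with the Pearson columns to within about one percentage point. The pooled figure depends on the borrowed lens effect: at r = 0.3 it is 89% with no lens effect and 71% with an effect of 1.5 SD. The MS-only figure does not depend on it.

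**B. Factor truly modifies the effect.** Slopes are in residual SD per SD of the factor; rates are simulated, 54 per arm.

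| Slope in SV, MS | Pooled | MS only | Interaction test |
|---|---|---|---|
| 0.5, 0 | 63% | 5% | 71% |
| +0.3, −0.3 | 6% | 57% | 85% |

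In the first row the MS-only correlation sees nothing, because the slope there is flat. In the second the slopes cancel when pooled. Where a Pearson test does reject, it still cannot separate modification from prognosis.

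**C. Power of the replacement.** The standard error of a slope difference is about √(2/54) = 0.192 residual SD. The difference detectable with 80% power at 5% is (1.960 + 0.842) × 0.192 = 0.54 residual SD per SD of the factor. The same formula gives 0.60 at 43 per arm and 0.42 at 90.

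**The case against.** **The analysis is supplementary and openly described.** It sits with the choroidal-response analyses, states that its measure is axial elongation, and serves no listed aim; no subgroup claim is planned. This stands, and it limits the importance of the point. It does not make the correlation answer the question that the sentence poses.

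**The size is driven by assumptions.** This stands too. Nothing in the documents shows that pupil size or peripheral refraction predicts elongation, and at zero correlation there is no excess of false positives. The mismatch between question and method does not depend on the assumed values.

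**Correlations by arm would be informative.** Partly so. The plan does not exclude them, but it sets out no comparison between arms, and correlations, unlike slopes, also depend on the spread within each arm.

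**A stronger reading.** A reader might infer that point 2 has the same fault, so that the MANOVA cannot say whether age, gender or initial refraction alters the lens effect. The documents do not support this. Point 2 asks about "Multivariate analyses of variance are used to examine the effect on treatment outcomes of various factors", and the plan uses outcomes to mean changes in SER and axial length. That can be read as a prognostic question, which a factor main effect answers. MANOVA can also carry group-by-factor terms. What can be said is that the model terms are not given.

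**Testing many interactions creates its own problem.** This stands. Section 4.8.2 has pupil diameter measured under several illuminations and at distance and near, and peripheral refraction at 10, 20 and 30 degrees nasally and temporally, repeated at five visits. Any replacement must fix the measures in advance.

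**Conclusion.** The concern holds for point 3. A Pearson correlation of pupil size or peripheral refraction with elongation measures prognosis and cannot show how the MS–SV difference varies. No lens-by-factor interaction is prespecified anywhere in the plan.

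The potential for error is large if these factors are prognostic (83% pooled, 60% within MS wearers at an assumed correlation of 0.3) and absent if they are not. These rates assume 54 completers per arm, a 5% level, normally distributed data and, for the pooled rate, a lens effect taken from SER rather than axial length.

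The point does not extend to a fault in the MANOVA of point 2, which at most lacks detail. It leaves the primary SER comparison, the between-group axial-length comparison and the sample size untouched. It is a cheap improvement to an exploratory analysis, not a threat to the trial's main conclusion.

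**What to change.** Replace the point 3 correlation for pupil size and peripheral refraction with, for each factor:

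24-month axial length change = lens group + baseline factor (continuous) + lens group × baseline factor.

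- Name in advance one pupil-size measure (illumination and viewing distance) and one peripheral-refraction measure (eccentricity and field, or a defined summary). This gives two interaction tests.
- Use baseline values, since later ones may change with growth or lens wear. If on-treatment values were intended, say so and treat that as a separate descriptive question.
- Label the analysis exploratory. Report the interaction estimate with its confidence interval, and rest any statement about who benefits on that estimate.
- Keep Pearson coefficients as description, reported separately by group.
- In point 2, list the MANOVA terms and say whether the question is prognosis or effect modification. The interaction model is needed for age, gender and initial refraction only if statements about who benefits are to be made.

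**Cost.** A few lines of text and a little analysis, with no new measurements: Table 4.1 already schedules both factors at baseline. Power is modest, as the 0.54 residual SD figure shows, so fewer positive statements should be expected, and a non-significant interaction should not be read as proof of a uniform effect.

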## 5 CLINICAL EXAMINATION PROCEDURES BY MI

### 5.1 Introduction

In order to maintain the integrity of double masked study, clinical examination will comprise two sessions: Clinical Examination by masked MI (or masked optometrist) and UMI (unmasked optometrist). The MI will be responsible for obtaining the required key data.

#### Objectives:

- i. to collect required data
- ii. to provide Rx for contact lens prescription
- iii. to maintain integrity of double masked design

Summary of eye examination procedures and data collection

#### Without cycloplegia

- Determination of dominant eye
- Pupillary distance (PD)
- Subjective refraction
- Autorefractometry and kerometry
- Best corrected visual acuity
- Binocular vision tests: phoria tests, stereopsis
- Accommodative tests: amplitude of accommodation, lag of accommodation
- Pupil diameters under different illumination, during distance and near viewing
- Non-contact IOP
- Subfoveal choroidal thickness (SFCT) by Spectral Domain Optical Coherence Tomography (SD-OCT)
- 

#### With cycloplegia

- Subjective refraction (as reference for the prescription of contact lenses)
- **Objective refraction:** autorefractometry
- **AL measurement:** measured by IOL Master (Carl Zeiss). Five measurements were taken and averaged.
- Peripheral refraction: measured by using a Shin-Nippon N-Vision-K 5001 autorefractor at center and 10, 20 and 30 degrees at the nasal and temporal visual field across the horizontal meridian.
- Dilated fundus examination

One drop of proparacaine 0.5% and then 1-2 drops of cyclopentolate HCL 1 % will be instilled to induce cycloplegia. Cycloplegic refraction will be measured by the open-field autorefractor (Shin-Nippon N-Vision-K 5001 autorefractor). Five measurements are obtained for each eye. The SER of the representative value from these 5 readings was used for statistical analysis. AL will be measured by IOL Master (Carl Zeiss) Five measurements will be taken and then averaged.

## 5.2 Determination of dominant eye

### Procedures:

- i. Ask subject to make a circle with thumbs and first fingers
- ii. Hold arms straight in front and view the spot light
- iii. Researcher to occlude each eye in turn to determine which eye is seeing the letter with habitual glasses

## 5.3 PD measurement

Shin-nippon PD-82 will be used to measure monocular and binocular PDs.

### Procedures:

[figure not shown]
- i. Turn the target distance lever to infinity.
- ii. Press the main switch.
- iii. Apply the instrument to the subject's forehead and nose, using the forehead rest and the nose rest.
- iv. Instruct the subject to look at the fixation target inside the instrument
- v. Slide either of the PD levers for right and or left, and match the PD pointer with the bright point reflecting on the subject's pupil.
- vi. Read the digital values (in mm) shown on the display window on the instrument top. The value in the center shows the interpupillary distance. The values R and L indicate the distances from the nose center to the right and left pupils respectively. Record PD, RPD and LPD.
- vii. Measure near PD. Set the target distance lever to 40cm and repeat step iv. – vi

## 5.4 Non-cycloplegic Autorefractometry and keratometry

The Shin-Nippon NVision-K 5001 autorefractor will be used to measure Rx objectively.

### Procedures:

- i. Set the measurement mode into 'R' and 'K' that allows to measure the autorefractometry and corneal curvature/ power at the same time.
- ii. Place the fixation target (Figure 5.1) 6 m from the machine.
- iii. Vertex distance is set to 12 mm.
- iv. The subject's chin is set on the chin rest and his/her forehead against the forehead rest.
- v. The subject should be able to see the fixation target in front of him/her through the "wide view" window.

### Figure 5.1 Fixation target

- vi. Ask the subject to look at the white circle in the middle of the fixation target (Figure 5.1).

[figure not shown]

Figure 5.2 Reticle circles and corneal reflex spot

- vii. While viewing the right eye on the CRT screen, carry out alignment: position the reticle circles so that they are both completely located inside the boundary of the pupil. (Figure 5.2)
- viii. The subject will see a faint red on the “wide view” window once the start button is pressed, and the subject will be requested to report the target position relative to the red ring.
- ix. The target will be adjusted as necessary until it is judged to be located at the centre of the red ring. The non-tested eye is then uncovered.
- x. Carefully maneuver the joystick to reduce corneal reflex spots to their smallest size. Press the button on the joystick to start measurements.
- xi. **Five measurements** will be taken.
- xii. Repeat the step vi. – xi. for the left eye.
- xiii. Press PRINT key and attach the printout to the record sheet.
- xiv. Record the **representative value** as the result of auto-refraction which is under the dashed line in the printout, for both eyes.

## 5.5 Subjective Refraction

### Procedures:

- i. Starting with autorefraction obtained above, refine subjectively.
- ii. Occlude the left eye.
- iii. Determine best sphere first.  
Add +0.25D and ask if “worse or the same”. If “the same” add +0.25D and repeat until the answer “worse” is given. If “worse” add -0.25D and ask if “better or the same”. If “better” add -0.25D and check for improvement in VA; repeat until the answer given is “the same”. Do not add the -0.25 D at this stage.
- iv. Determine cylindrical error.  
Add -0.25D to best sphere and carry out cross-cylinder. Check axis and then power. Using a non-directional letter as a target.

- v. Refine sphere using +1.00D blur back test monocularly and finish by offering a binocular +0.25D add. Give this if “no difference”. Stop if “worse”. Repeat until “worse”.
- vi. Binocular balance (prism dissociation): with the monocular subjective result in the phoropter, add +1.00D to each eye, then add 3Δ base-down OD and 3Δ base-up OS. Use the 0.3 logMAR line as the target. If the upper line letter appears clearer than the lower line letters, add +0.25D to right eye. If the lower line letters appear clearer than the upper line, add +0.25D to left eye. Stop when no difference between the upper and lower line.

### **5.6 Visual acuity**

- Distance VA, including BCVA of both eyes will be assessed using Logarithmic 2000 series ETDRS Chart and Low Contrast ETDRS Charts at 4 m (Precision Vision Inc.) with the illuminator cabinet (450 cd/m^2).
- Near VA (40cm) will be measured by the Near Vision Test Card from the Hong Kong Polytechnic University.

### **5.7 Phoria measurement**

#### **Procedures:**

- i. Howell phoria card will be used to measure phoria
- ii. Insert 6Δ base down right eye into the trial frame with the best subjective refraction
- iii. Phoria at distance is measured by asking the subject to indicate the number on the bottom line that is nearest to the top arrow, when viewing the large phoria chart at 3 m. Always ask the subject to keep the letters clear.
- iv. The blue even numbers indicate exophoria and the yellow odd numbers indicate esophoria
- v. Phoria at near is measured by asking the subject to indicate the number on the bottom line that is nearest to the top arrow, when viewing the small phoria chart at 33 cm. Always ask the subject to keep the letters clear.
- vi. Record the distance and near phoria (-ve: exo; +ve: eso)

### **5.8 Stereopsis**

Stereoacuity (minute of arc) will be measured with Randot Stereotest (refer to user guide) at 40 cm with Polaroid goggles.

### **5.9 Amplitude of accommodation**

Amplitude of accommodation (D) will be measured with RAF ruler for monocularly and binocularly. Average of 3 measurements will be used for data analysis.

## **5.10 Lag of Accommodation**

### **Procedures:**

- i. Place the subject's best subjective refraction in the trial frame and position the subject in the Shin-Nippon NVision-K 5001 autorefractor.
- ii. Place the distance target (0 logMAR letters) at 6 m. While encouraging the subject to look clear the letters, take 5 readings on the subject's right eye, followed by 5 readings on the left eye. The eye not being measured will be occluded.
- iii. Place the near target (0 logMAR letters) at 33 cm (3D near stimulus). While encouraging the subject to look clear the letters, take 5 readings on the subject's right eye, followed by 5 readings on the left eye. The eye not being measured will be occluded.
- iv. The lag of accommodation will be calculated for each eye by summing the difference in the mean spherical equivalents between the 5 distance readings and the 5 near readings and 3D (matrix is also used in calculation).

### 5.11 Choroidal thickness measurement

Choroidal thickness measurement will be measured at the following schedule (please refer to Table 4.1):

- Baseline visit
- Delivery of 1st pair of CL, 2 week of CL wear, 1 month of CL wear, 3 month of CL wear
- 6-month FU, 12-month FU, 18-month FU and 24-month FU.

Choroidal thickness will be obtained by a modified dual wavelength Spectral Domain Ocular Coherence Tomographer (SD-OCT) by Heidelberg Engineering (Spectralis HRA+OCT, Heidelberg Engineering, Germany) using enhanced depth imaging mode and with the help of 1060nm. This OCT uses a dual light source of 870nm and 1060nm at scanning speed of 40000A-scan/second. Cross sectional images with axial resolution of 3.9 $\mu$ m and transverse resolution of 14 $\mu$ m will be obtained. Choroid in an OCT image is defined as the boundary between the highest reflected interfaces from retinal pigmented epithelium to the chorio-scleral junction. The choroidal thickness is determined using the built-in software of SD-OCT (Heidelberg Eye Explorer) automatically. Subfoveal and parafoveal choroidal thickness at 1mm and 3mm away from the fovea in temporal, nasal, superior and inferior quadrants will be measured. The changes in choroidal thickness are compared between the MS lens and the SV groups.

To avoid diurnal variation of CT, we will arrange data collection for subject at similar time in each follow-up visit if possible.

### 5.12 IOP and cycloplegia

- i. Measure non-contact IOP using Nidek NT-4000. Excluded if IOP > 22 mm Hg and CD ratio >0.6.
- ii. Explain purpose of eyedrops to parent. Handout sheet stating normal reaction will be given to the parent with telephone numbers. Ask to contact if any different reaction occurs.
- iii. Cycloplegia is induced by instilling 1 drop proparacaine (0.4%) then 2 drops cyclopentolate HCL (1%) into each eye at 5-minute intervals. Subject is asked to hold puncta.

### 5.13 Cycloplegic Autorefraction

#### Procedures:

- iv. 30 minutes later check pupils. If dilated, measure amplitude of accommodation using push-up method. If not dilated add one further drop of cyclopentolate to each eye.
- v. Autorefract when **accommodation <2.00D**.

- vi. Carry out autorefractometry using Shin-Nippon NVision-K 5001 (open-field) autorefractor as in **Non-cycloplegic Autorefractometry section**. Five **measurements** are obtained for each eye.
- vii. The SER of the representative value of will be used for statistical analysis.

#### 5.14 Axial Length Measurement with will be used

The Zeiss IOL Master will be used to measure axial length.

##### Procedures:

- i. Press  bottom to input new subject data or select old subject data.
- ii. Finished entering then press <NEW> button. This will automatically activate the “Overview” mode.
- iii. The fixation light and the illumination LEDs are on
- iv. Align the eyes with the red marks on the side rails of the headrest.
- v. Ask the subject to look at the yellow fixation light in the middle
- vi. Adjust the instrument until the 6 light spots appear focused on the screen.
- vii. The circle of lights should be approximately centered to the pupil and cross hairs
- viii. Then push button on the joystick
- ix. Make sure “phakic” mode is on. It can be checked in the AL Setting in the screen
- x. The instrument now automatically changes the magnification: a smaller section of the eye becomes visible with the reflection of the alignment light and vertical line.
- xi. Ask the subject to look at the red fixation light. On the display, a crosshair with a circle in the middle appears.
- xii. Fine-align the instrument so that the reflection of the alignment light appears within the circle
- xiii. Push the button on the joystick to start the measurement
- xiv. By pressing the button on the joystick continuously, next measurements will be started.
- xv. If the result of one measurement differs by more than 0.2mm from the others, an “Evaluation” message will be displayed in place of the average.
- xvi. If the signal received by the instrument was poor, an exclamation mark will be shown besides the value of that measurement.
- xvii. All the value marked with special marking as stated above will be deleted.
- xviii. Five consecutive readings were made for each measurement; each reading showing signal-to-noise ratio above 2.0 and differing by less than 0.20 mm from the others. Any reading which not fit the criterion was deleted and re-measured. (Not more than 20 measurements can be taken on each eye per day).
- xix. Record the mean axial length in mm.

